6.2 Part 2: Subjects with ESRD

Study Procedures ^a	S ^b Days → Hours →	Study Days in Period 1 of Part 2 ^c																				
		-2 /-1		1																		
		(C-D) ^d	P	0	0.25	0.5	1	2	2.5	3	3.5	4	4.5	5	5.5	6	8	12	16 ^e	24	36	48
Administrative Procedures																						
Informed Consent		X																				
Informed Consent for Future Biomedical Research		X																				
Inclusion/Exclusion Criteria		X	X																			
Medical History		X																				
Safety Evaluations																						
Full Physical Examination ^f		X																				X
Height		X																				
Weight		X	X																			
12-Lead Electrocardiogram		X		X ^g																		X
Vital Signs (heart rate & blood pressure)		X		X ^g				X														X
Vital Signs (respiratory rate & temperature)		X																				
Hematology, Serum Chemistry ^h , and Urinalysis		X	X																	X		X
Serum Pregnancy Test (female subjects only)		X	X																			
Serum FSH (postmenopausal females only)		X																				
Urine or Saliva Drug Screen		X	X																			
Urine or Breath Alcohol Screen		X	X																			
HIV/Hepatitis Screen		X																				
Adverse Events Monitoring																X						
Concomitant Medication Monitoring															X							
Study Drug Administration / Pharmacokinetics																						
MK-7264 Administration				X ⁱ																		
Blood for MK-7264 Pharmacokinetics			X		X	X	X	X	X	X	X	X	X	X	X	X	X	X	X	X	X	X ^j
Urine for MK-7264 Pharmacokinetics ^k			X													X						
Other Procedures																						
Blood for Genetic Analysis ^l				X																		
Confinement in the CRU																X						
Visit		X																				

Study Procedures ^a	Study Days in Period 2 of Part 2 ^c																		FU ^g			
	Days →		Hours →																			
	-2 / -1	(C-I) ^d	P	0	0.25	0.5	1	2	2.5	3	3.5	4	4.5	5	5.5	6	8	12	16 ^e	24	36	48
Safety Evaluations																						
Full Physical Examination ^f																						X ^p
12-Lead Electrocardiogram				X ^g																		X ^p
Vital Signs (heart rate & blood pressure)			X ^g				X															X ^p
Vital Signs (respiratory rate & temperature)																						
Hematology, Serum Chemistry ^h , and Urinalysis		X																	X			X ^p
Urine or Saliva Drug Screen		X																				
Urine or Breath Alcohol Screen		X																				
Adverse Events Monitoring																X						
Concomitant Medication Monitoring															X							

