Study Drug Administration / Pharmacokinetics																						
MK-7264 Administration			X																			
Blood for MK-7264 Pharmacokinetics		X		X	X	X ^m	X	X	X	X												
Urine for MK-7264 Pharmacokinetics ^k		X															X					
Dialysate for MK-7264 Pharmacokinetics ⁿ							X	X	X	X	X	X	X	X	X	X	X					
Other Procedures																						
Hemodialysis ^o																X						
Confinement in the CRU																X						
Visit																						

- a. For details on Procedures, refer to Section 10 and/or corresponding appendices.
- b. Within 28 days prior to the first study drug administration.
- c. There will be a washout period of approximately 7 days (with 3 dialysis sessions) between MK-7264 dosing in Period 1 and Period 2.
- d. Subjects will be admitted to the CRU on Day -2 or Day -1, at the time indicated by the CRU.
- e. The 16-hour time point following dosing on Day 1 will be either on Day 1 or Day 2, depending on the time of dosing on Day 1.
- f. A symptom-driven physical examination may be performed at other times, at the Investigator's discretion.
- g. To be performed within 24 hours prior to dosing.

- h. Samples for serum chemistry will be obtained following a fast of at least 8 hours; however, in case of dropouts or rechecks, subjects may not have fasted for 8 hours before the serum chemistry sample is taken.
- i. To be administered immediately following scheduled HD.
- j. If the next scheduled HD must be initiated before 72 hours postdose, a sample for MK-7264 analysis will be collected prior to HD.
- k. Urine collection intervals are: pre-dose (spot collection), 0 - 12 hours, 12 - 24 hours post-dose, and 24 -48 hours. Urine samples will be collected whenever possible, as some subjects with ESRD may not be able to produce urine at each interval. For subjects who are anuric, urine samples for urinalysis will not be collected.
- l. This sample should be drawn for planned analysis of the association between genetic variants in DNA and drug response. This sample will not be collected at the site if there is either a local law or regulation prohibiting collection, or if the IRB/IEC does not approve the collection of the sample for these purposes. If the sample is collected, leftover extracted DNA will be stored for future biomedical research if the subject signs the FBR consent. If the planned genetic analysis is not approved, but FBR is approved and consent is given, this sample will be collected for the purpose of FBR.

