9.1.2 Study Duration

The duration of Part 1 of the study from screening to Day 4 is approximately 4.5 weeks. The duration of Part 1 of the study from screening to follow-up is approximately 6 weeks.

The duration of Part 2 of the study from screening to Day 4 of Period 2 is approximately 5.5 weeks. The duration of Part 2 of the study from screening to follow-up is approximately 7 weeks.

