9.2 Selection of Study Population

9.2.1 Inclusion Criteria

9.2.1.1 Subjects with Moderate or Severe Renal Insufficiency or with ESRD

Subjects must fulfill all of the following inclusion criteria to be eligible for participation in the study, unless otherwise specified:

1. Adult male or female subject, 18-80 years of age, inclusive, at screening.
2. Subject is a non-smoker or moderate smoker (≤ 20 cigarettes/day or the equivalent). Subject must agree to consume no more than 10 cigarettes or equivalent/day from the time of screening and throughout the period of sample collection.
3. Subject has a body mass index (BMI) ≥ 18.5 and $\leq 40.0 \text{ kg/m}^2$, at screening.
4. Females be non-pregnant, non-breast feeding and:
 - a. If with reproductive potential: subject must demonstrate a serum β -human chorionic gonadotropin (β -hCG) level consistent with the nongravid state at screening and agree to use (and/or have their partner use) two (2) acceptable methods of birth control beginning at screening, throughout the study and until 2 weeks after the last dosing of study drug. Combination method (requires use of two of the following):
 - diaphragm with spermicide (cannot be used in conjunction with cervical cap/spermicide and contraceptive sponge)
 - cervical cap with spermicide (nulliparous women only)
 - contraceptive sponge (nulliparous women only)
 - male condom or female condom (cannot be used together)
 - b. If postmenopausal: subject is without menses for at least 1 year and have a documented follicle stimulating hormone (FSH) level in the postmenopausal range at screening.
 - c. If surgically sterile: subject is status post hysterectomy, oophorectomy, or tubal ligation.

NOTE: These procedures must be confirmed with medical records. In the absence of documentation, hysterectomy may be confirmed by pelvic exam or if necessary by ultrasound; oophorectomy may be confirmed by hormone levels, particularly FSH in the postmenopausal range, but tubal ligation subjects without records should be excluded. Information must be captured appropriately within the site's source documents.

5. A subject understands the study procedures in the informed consent forms (ICFs), is willing and able to comply with the protocol, and provides written informed consent for the trial. Future Biomedical Research participation is voluntary and is not required in order to participate in the trial.

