9.2.3 Subject Withdrawal/Discontinuation Criteria

Subjects may withdraw consent at any time for any reason or be dropped from the trial at the discretion of the Investigator should any untoward effect occur. In addition, a subject may be withdrawn by the Investigator or the Sponsor if enrollment into the trial is inappropriate, the trial plan is violated, or for administrative and/or other safety reasons. Specific details regarding discontinuation or withdrawal procedures, including specific details regarding withdrawal from Future Biomedical Research, are provided in [Section 9.2.3.1](#).

Discontinuation is “permanent”. Once a subject is discontinued, he/she shall not be allowed to enroll again.

Subjects may be replaced at the discretion of the Sponsor.

A subject must be discontinued from the study for any of the following reasons:

- The subject withdraws consent.
- The subject has a confirmed positive serum pregnancy test.
- The subject has a medical condition or personal circumstance which, in the opinion of the Investigator and/or Sponsor, places the subject at unnecessary risk through continued participation in the trial or does not allow the subject to adhere to the requirements of the protocol.

A subject may be discontinued from the study for any of the following reasons:

- Adverse events.
- Difficulties in blood collection.
- Protocol violation (other than those listed above).
- If a subject vomits within 3 hours after dosing, i.e., a period of time equal to two times the Tmax of MK-7264, he/she may be withdrawn from the study. The clinical report will include reasons for subject withdrawals as well as details relevant to the subject's withdrawal.

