10 STUDY PROCEDURES

The Study Events Flow Chart ([Section 6](#)) summarizes the clinical procedures to be performed at each visit. Individual clinical procedures are described in detail below. Additional evaluations/testing may be deemed necessary by the Investigator and/or the Sponsor for reasons related to subject safety.

For this study, the blood collection for MK-7264 is the critical parameter and needs to be collected as close to the exact time point as possible. All other procedures should be completed as close to the prescribed/scheduled time as possible, but can be performed prior or after the prescribed/scheduled time.

Any nonscheduled procedures required for urgent evaluation of safety concerns take precedence over all routine scheduled procedures.

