10.1.6 Laboratory Tests

All tests listed below will be performed as per Study Events Flow Chart ([Section 6](#)). In addition, laboratory safety tests may be performed at various unscheduled time points, if deemed necessary by the Investigator.

Hematology

- Hemoglobin
- Hematocrit
- Total and differential leukocyte count
- Red blood cell count
- Platelet count

Serum Chemistry*

- Blood urea nitrogen
- Bilirubin (total and direct)
- Alkaline phosphatase
- Aspartate aminotransferase (AST)
- Alanine aminotransferase (ALT)
- Albumin
- Sodium
- Potassium
- Chloride
- Glucose (fasting)
- Creatinine**

Urinalysis [¥]

- pH
- Specific gravity
- Protein***
- Glucose
- Ketones
- Bilirubin
- Blood***
- Nitrite***
- Urobilinogen
- Leukocyte esterase***

Additional Tests

- HIV test
- HBsAg
- HCV
- Urine or saliva drug screen
 - Opiates
 - Amphetamines
 - Barbiturates
 - Benzodiazepines
 - Cocaine
 - Cannabinoids
- Urine or breath alcohol screen
- Serum pregnancy test (for females only)
- FSH (for postmenopausal females only)

* Serum chemistry tests will be performed after at least an 8-hour fast; however, in case of dropout or rechecks, subjects may not have fasted for 8 hours before the serum chemistry sample is taken.

** At screening, eGFR will be calculated based on MDRD for renal classification assignment. Baseline eGFR will be obtained twice and the mean of the two values will be used for group assignment in Part 1 of the study.

*** If urinalysis is positive for protein, blood, nitrite and/or leukocyte esterase, a microscopic examination (red blood cell, white blood cell, bacteria, casts, and, epithelial cells) will be performed.

¥ Any unexplained drug-related hematuria or evidence of triphosphate crystals should be referred to a nephrologist

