10.1.7.2 Reporting of Pregnancy and Lactation to the Sponsor

Although pregnancy and lactation are not considered adverse events, it is the responsibility of Investigators or their designees to report any pregnancy or lactation in a subject (spontaneously reported to them) that occurs during the trial.

Pregnancies and lactations that occur after the consent form is signed but before allocation must be reported by the Investigator if they cause the subject to be excluded from the trial, or are the result of a protocol-specified intervention, including but not limited to washout or discontinuation of usual therapy, diet, treatment or a procedure. Pregnancies and lactations that occur from the time of allocation through 14 days following cessation of Sponsor's product must be reported by the Investigator. All reported pregnancies must be followed to the completion/termination of the pregnancy. Pregnancy outcomes of spontaneous abortion, missed abortion, benign hydatidiform mole, blighted ovum, fetal death, intrauterine death, miscarriage and stillbirth must be reported as serious events (Important Medical Events). If the pregnancy continues to term, the outcome (health of infant) must also be reported.

Such events must be reported within 24 hours to the Sponsor either by electronic media or paper. Electronic reporting procedures can be found in the EDC data entry guidelines. Paper reporting procedures can be found in the Investigator Trial File Binder (or equivalent).

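### Minor safety point: ESRD women have no scheduled serum pregnancy test at Period 2 check-in, so the last scheduled test is nominally 8–9 days old at the second dose

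*Protocol*

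**What the plan says.** Protocol 6.1 schedules a serum pregnancy test at screening and again at check-in, before the single Part 1 dose. In 6.2 the Period 1 chart does the same under the row "Serum Pregnancy Test (female subjects only". The Period 2 chart in 6.2 has no pregnancy row. At check-in it marks hematology, chemistry and urinalysis, the drug screen and the alcohol screen. Footnote c sets the spacing: "There will be a washout period of approximately 7 days (with 3 dialysis sessions) between MK-7264 dosing in Period 1 and Period 2".

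Section 9.2.3 lists, among the reasons for which a subject must be discontinued: "The subject has a confirmed positive serum pregnancy test". Section 10.1.6 has the laboratory tests follow the flow chart and adds that "laboratory safety tests may be performed at various unscheduled time points, if deemed necessary by the Investigator". Section 10 says more generally: "Additional evaluations/testing may be deemed necessary by the Investigator and/or the Sponsor for reasons related to subject safety". Section 10.1.7.2 obliges the investigator "to report any pregnancy or lactation in a subject (spontaneously reported to them) that occurs during the trial". None of these schedules a test between the two doses.

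**The concern.** The sponsor scheduled a check-in pregnancy test before the only dose in Part 1 and before the first dose in Part 2, but not before the repeat dose in Part 2. A woman whose pregnancy was too early to show at Period 1 check-in would receive the second 50 mg unless someone chose to test her. The discontinuation rule depends on a positive serum test, and between the doses no scheduled test can produce one. What is at stake is a possibly avoidable second exposure in early pregnancy. The pharmacokinetic comparison of dialysis with non-dialysis dosing is not at stake.

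**Working it through.** **Inputs (Protocol)**
- Check-in is on Day -2 or Day -1, so 1–2 days before the Day 1 dose (6.2, footnote d).
- The Period 1 and Period 2 doses are about 7 days apart (6.2, footnote c).
- Screening falls within 28 days before the first dose (6.2, footnote b).
- In each period subjects are housed from check-in until after the 72-hour blood draw (9.1.1), which is 3 days after dosing.
- Follow-up contact is about 14 days after the last dose (6.2, footnote q).

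**Reproducing the plan's own durations.** Section 9.1.2 states: "The duration of Part 2 of the study from screening to Day 4 of Period 2 is approximately 5.5 weeks". With the full screening window, 28 + 7 + 3 = 38 days, and 38 / 7 = 5.4 weeks. For screening to follow-up, 28 + 7 + 14 = 49 days = 7.0 weeks, matching the stated 7 weeks. So the 7 days run from dose to dose. The 28 days are a maximum; a given woman may be screened later.

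**Check-in items, side by side**

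| Laboratory item at check-in | Part 1 | Part 2 Period 1 | Part 2 Period 2 |
|---|---|---|---|
| Safety laboratory tests | yes | yes | yes |
| Drug screen | yes | yes | yes |
| Alcohol screen | yes | yes | yes |
| Serum pregnancy test | yes | yes | no row |

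The Period 2 chart keeps a row with no mark at all (respiratory rate and temperature), so a pregnancy row lost in reproduction is unlikely.

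**Age of the last scheduled test at the Period 2 dose.** Age = (days from Period 1 check-in to Period 1 dose) + (days between doses).
- Check-in on Day -1: 1 + 7 = 8 days.
- Check-in on Day -2: 2 + 7 = 9 days.
- If the approximate 7 days is assumed to mean 6–8, the range is 1 + 6 = 7 to 2 + 8 = 10 days.

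For the Part 1 dose and the Period 1 dose the age is 1–2 days.

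**Time outside the unit between periods.** Days outside = 7 − 3 − (1 or 2) = 2–3 days. With 6–8 days between doses, the range is 6 − 3 − 2 = 1 to 8 − 3 − 1 = 4 days. A conception outside the unit in that gap would be only days old at Period 2 check-in and might well be missed. The test would therefore mainly catch a pregnancy already present but undetectable at Period 1 check-in.

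**Blood volume.** Table 3 gives 12.5 + 8.5 + 6 × 12.5 + 58 × 3 = 12.5 + 8.5 + 75 + 174 = 270 mL. The six on-study draws match three safety-laboratory time points in each of two periods, and the table counts serum pregnancy inside those draws when it falls at the same time. A test at Period 2 check-in leaves 270 mL unchanged.

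**The case against.** The strongest case is that the omission is a deliberate and coherent choice. Period 2 continues an enrolled subject's participation. Its chart also drops the eligibility check and weight at check-in. The eligibility text ties the negative β-hCG to screening, whereas the drug and alcohol exclusion applies at screening or check-in, and those two screens do recur. Nothing in the protocol promises a test before every dose. This explains how the chart may have come about, but the Period 1 check-in test also goes beyond the β-hCG criterion, so the protocol did treat a test shortly before dosing as worthwhile.

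The mitigations are real. Women of reproductive potential must use "two (2) acceptable methods of birth control beginning at screening, throughout the study and until 2 weeks after the last dosing of study drug". Two scheduled tests precede the first dose, and confinement covers most of the interval between doses. They narrow the gap without closing it. The methods listed in 9.2.1.1 are all barrier methods. Because screening may fall well under 28 days before the first dose, a woman could have conceived before contraception was required and still test negative twice. The documents do not say how often that would happen.

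Harm is not shown. The first 50 mg would already have been given, and the protocol leaves toxicology to the Investigator's Brochure. That stands, and it limits the point to a minor one.

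A reader might go further and infer that the plan contradicts its own discontinuation rule, or that no test is possible between the doses. Neither follows. Section 9.2.3 acts on a confirmed positive test whenever one is obtained, and sections 10 and 10.1.6 allow one to be ordered.

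**Conclusion.** The gap holds as a minor participant-safety point. The Period 2 dose is the only dosing occasion without a scheduled check-in pregnancy test, and the last scheduled test is then nominally 8–9 days old, or 7–10 days if the spacing is taken as 6–8 days. This rests on the chart as printed and on a dose-to-dose reading of the washout, which the stated study durations support. The SAP's note in 9.7 that the washout held 2 dialysis sessions does not alter the 7 days.

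The benefit cannot be put as a probability. The documents give no sex or reproductive status for the ESRD group, no hCG detection lag and no pregnancy rate. A reader might count all 6 Period 2 doses as unprotected, but the test is irrelevant to men and to postmenopausal or surgically sterile women, and the relevant number may be zero. Nor do the documents suggest that anyone was harmed: SAP 9.8.3.1 reports no discontinuations and 10.1 reports that all 24 subjects completed. That shows no confirmed positive test ended participation; it does not show whether anyone was tested between doses. No endpoint, sample size or analysis changes.

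**What to change.** Add the serum pregnancy row for female subjects to the Period 2 chart in Protocol 6.2, with a mark at check-in (Day -2/-1). Run the test on the safety-laboratory blood already drawn there, and require the result to be reviewed before the Period 2 dose. Section 9.2.3 needs no change.

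The cost is one chart row and at most 6 assays, with no extra blood. The result must be back within the 1–2 days between check-in and dosing. The one real downside is that a positive result needing confirmation could delay a dose tied to a scheduled hemodialysis session. As this trial is complete, the change matters wherever the two-period schedule is reused.

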7 BACKGROUND AND RATIONALE

7.1 Background

P2X3 receptors are ligand-gated ion channels that respond to adenosine triphosphate (ATP) and are almost exclusively localized on C-fiber sensory neurons, including those that innervate the upper and lower airways. ATP is released by damaged, stressed, and inflamed tissues. ATP and P2X3 containing receptors have been shown to be involved in airways sensitization and their involvement provides a rationale for P2X3 antagonism in the treatment of chronic cough.

MK-7264, a selective P2X3 receptor antagonist, is the first clinical agent targeting this receptor, and is being evaluated for treatment of cough. Additionally, MK-7264 has been evaluated in asthma, interstitial cystitis/bladder pain syndrome, and osteoarthritis pain. P2X3 antagonists may address the unmet medical needs for any of these indications.

Refer to the Confidential Clinical Investigator's Brochure (IB) for detailed background information on MK-7264 in the following areas:

- Physical, Chemical, and Pharmaceutical Properties and Formulation
- Nonclinical Pharmacology
- Safety Pharmacology and Supplemental Safety Pharmacology Studies
- Pharmacokinetics and Product Metabolism in Animals
- Toxicology (Preclinical Safety Assessment)
- Effects in Humans and Clinical Experience

7.2 Rationale

7.2.1 Rationale for this Study and Study Design

Preliminary data indicate that MK-7264 is eliminated primarily through renal elimination with metabolism playing a secondary role in its elimination. Following multiple dose administration, approximately 60% of a 50 mg dose was excreted at steady state in healthy subjects. Thus, it is anticipated that in the setting of renal impairment, alterations in the pharmacokinetics of MK-7264 are likely and dose adjustments may be indicated. The need for dose adjustment is a clinically significant issue as the incidence of renal impairment is associated with increasing age, and the patient population in MK-7264-012, a Phase 2b chronic cough efficacy study, had a median age of approximately 60, though there was a wide range of ages from 22 to 79.

The potential impact of mild renal impairment was assessed in a previous Phase 1 multiple dose study in healthy and elderly adult male and female subjects, MK-7264-007, which included subjects with mild renal impairment. A non-population based preliminary pharmacokinetic analysis of this study investigated the impact of eGFR on exposures (AUC and Cmax) in elderly and non-elderly subjects using a linear fixed effect model. In this analysis, a subject with mild renal impairment (eGFR = 60 mL/min) in comparison to a subject with normal renal function (eGFR = 90 mL/min) would be predicted to have an increase of AUC0-t and Cmax of 19% and 11%, respectively, with a

300 mg dose at steady state. Age and gender did not appear to have an effect on the pharmacokinetics of MK-7264 independent of eGFR in this analysis.

Since MK-7264 is eliminated primarily through renal excretion, the impact of renal function on pharmacokinetics of MK-7264 will be extended beyond the previous experience in subjects with mild impairment to subjects with moderate and severe renal impairment as well as subjects with ESRD. The relationship between renal function (as measured by eGFR) and exposure (as measured by AUC) will be explored by comparing the pharmacokinetics in within-study control subjects with normal renal function to those with varying degrees of renal impairment. The study will also examine the degree to which MK-7264 is removed from plasma by hemodialysis. The safety and tolerability of MK-7264 when administered in subjects with renal impairment will also be assessed. The control subjects will be matched by age (mean within \pm 10 years) and body weight (mean \pm 10 kg) to the mean age and body weight of pooled moderate and severe renal impairment subjects, as recommended by the draft FDA Guidance (Guidance for Industry: Pharmacokinetics in Patients with Impaired Renal Function Study Design, Data Analysis, and Impact on Dosing and Labeling; issued March 2010)¹.

